Hypothesis B: Activating the campaign will significantly increase the number of FEP referrals and patients admitted to OTNY as compared to number of FEP referrals and patients admitted pre-campaign. All OTNY referral data are thoroughly recorded as part of treatment as usual and stored in a centralized database within OTNY central. Extracted information includes the name and contact details of the individual making the inquiry, reason for the inquiry, presenting symptoms, duration of symptoms, age of the prospective patient, and outcome of the referral including OTNY intake/acceptance or screen out. For the duration of the award, all de-identified referral data routinely uploaded to OTNY central will be provided to research staff for analyses. We will extract OTNY referral data from each site prior to activing the campaign to serve as baseline, and will continue to extract all OTNY inquiry data during the active campaign. Additional referrals arriving through dedicated campaign channels (email, phone calls, text, live chat, and two way video) will be recorded centrally by research staff. All FEP referrals will be provided an appointment for an evaluation at the nearest OTNY program and admission to the program will be recorded. All ineligible referrals will be referred to appropriate local services. Based on existing OTNY inquiry data as well as the results of our prior pilot initiatives, we anticipate approximately doubling weekly inquiries as a result of the campaign, arriving through campaign related channels over the course of the trial (30 additional referrals). Of those, we anticipate that 20% will be appropriate for OTNY (6 participants weekly) and that 4 of those individuals will be successfully enrolled each week as a result of the campaign. We will compare baseline rates of inquiries, number of FEP referrals, and number of patients admitted to OTNY in NYS prior to campaign activation, to rate of inquiries, number of FEP referrals, and number of patients admitted to OTNY in NYS while the campaign is active both arriving through the campaign, and traditional referral channels.

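### Hypothesis B counts inquiries and FEP referrals from OTNY central alone at baseline but from OTNY central plus a campaign log in active periods, so ascertainment changes with treatment and FEP referrals can be counted twice

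*Combined protocol and SAP*

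**What the plan says.** All of this is in Section 12 (Statistical Analysis), under Hypothesis B, unless noted.

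- Baseline source: "We will extract OTNY referral data from each site prior to activing the campaign to serve as baseline".
- Active period, first source: staff "will continue to extract all OTNY inquiry data during the active campaign".
- Active period, second source: "Additional referrals arriving through dedicated campaign channels (email, phone calls, text, live chat, and two way video) will be recorded centrally by research staff".
- Comparison: baseline inquiries, FEP referrals and admissions are set against the same three quantities "while the campaign is active both arriving through the campaign, and traditional referral channels".
- Overlap between the sources: "All FEP referrals will be provided an appointment for an evaluation at the nearest OTNY program and admission to the program will be recorded". On the OTNY side, "All OTNY referral data are thoroughly recorded as part of treatment as usual and stored in a centralized database within OTNY central".
- Form of the data: "all de-identified referral data routinely uploaded to OTNY central will be provided to research staff for analyses". The same paragraph lists name and contact details among the extracted items, so it is unclear whether records from the two sources could be matched.
- Counting unit: under Aim 3, research staff log every contact, and users may come back without limit.
- Follow-up of campaign referrals: Section 24 relies on permission to re-contact people about their enrolment, not on record linkage.

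The hypothesis sentence itself (Section 4, repeated in Section 12) names FEP referrals and admitted patients. Inquiries enter only in the later description of the comparison. The plan gives no matching key, no de-duplication rule and no common definition of an inquiry or an FEP referral across the two sources.

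**The concern.** A stepped wedge compares control and active cluster-periods on the same outcome. Here, two of the three quantities are ascertained differently in the two conditions. The campaign's contact channels operate only where the campaign does, so the extra source switches on with the treatment indicator in each cluster. Randomised order, period effects and cluster random effects do not help, because the change in measurement and the campaign effect share the same column of the design matrix.

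Two consequences follow. First, the inquiry comparison is not like-for-like: contacts made through a new channel are added to a baseline that had no equivalent. Second, an FEP referral that comes through the campaign can enter the staff log and then the OTNY record when the person is sent for evaluation. Counting both would inflate a real effect, or create one if the campaign merely re-routes people whom OTNY would have received anyway.

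**Working it through.** **Inputs.** Sections 8 and 12: 34 OTNY referrals a week, 26% found eligible, 8 enrolled. Expected from the campaign: 30 additional referrals a week, 20% appropriate (6), 4 enrolled. Section 12, Aim 2: 12 of 24 cluster-periods have the campaign.

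**Reproducing the plan's figures.** 30 x 0.20 = 6, as stated. (34 + 30)/34 = 1.88, consistent with an approximate doubling. No sample size or power is given for Hypothesis B, so there is none to reproduce.

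**Inquiries.** The expected change is from 34 to 64 a week (+88%), and all 30 come from the source that is empty at baseline. If a share s of campaign contacts replaces traditional inquiries, the ratio is (34 + 30 - 30s)/34:
- s = 0: 64/34 = 1.88
- s = 0.5: 49/34 = 1.44
- s = 1: 34/34 = 1.00

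If nothing is displaced and the 6 FEP referrals also appear in the OTNY extract, the ratio is 70/34 = 2.06.

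**FEP referrals, with the plan's expected effect.** The plan states no baseline FEP-referral count. I take it as the referrals found eligible: 34 x 0.26 = 8.84 a week (an assumption). Let d be the share of the 6 campaign referrals counted twice. The documents do not give d, so the range is 0 to 100%. Apparent ratio = (8.84 + 6 + 6d)/8.84:
- d = 0: 14.84/8.84 = 1.68
- d = 0.25: 16.34/8.84 = 1.85
- d = 0.5: 17.84/8.84 = 2.02
- d = 1: 20.84/8.84 = 2.36

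**FEP referrals, with no true effect.** Suppose all 6 are people OTNY would have received anyway, so the true ratio is 1.00. Apparent ratio = (8.84 + 6d)/8.84:
- d = 0.25: 10.34/8.84 = 1.17
- d = 0.5: 11.84/8.84 = 1.34
- d = 1: 14.84/8.84 = 1.68

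**Consequence for a test (illustration only).** Assume equal cluster volumes and 26-week periods. Each arm of the comparison then has 12 x 26/6 = 52 statewide weeks. With no true effect and d = 0.25, the counts are 52 x 8.84 = 460 and 52 x 10.34 = 538. For Poisson counts, z = ln(538/460)/sqrt(1/460 + 1/538), about 2.5, which gives about a 69% chance of rejecting at two-sided 0.05. The chance is about 17% at d = 0.10 and above 99% at d = 0.5. This ignores clustering. A mixed model would reject less often, but the bias in the ratio would be the same.

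**Admissions.** Admission is an OTNY event recorded in both conditions. The expected change from 8 to 12 a week (ratio 1.50) can be counted from OTNY records throughout.

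**The case against.** The strongest case against is that double counting is inferred, not planned. Section 12 calls the campaign contacts additional and splits active-period counts by channel, which can be read as one channel per person. The campaign lines are distinguishable, and eligibility follows one set of OTNY criteria (Section 7). That reading is reasonable, but no rule enforces it. De-identified OTNY data and follow-up by re-contact leave it open whether the two sources could be reconciled.

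Four stronger readings are tempting, and the documents do not support them.

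- *Inquiries must rise whatever the campaign does.* They need not: the combined count stays flat if traditional inquiries fall one-for-one and nobody is counted twice. Contacts from people who would not otherwise have come forward are also part of what the campaign is for. The +88% is the plan's expected effect, and nothing in the documents divides it into effect and artefact.
- *The FEP-referral count doubles.* At full duplication the count rises from 14.84 to 20.84, or 40%. Only the increment doubles, from 6 to 12.
- *All of Hypothesis B is compromised.* Admissions, one of its two named outcomes, are largely untouched, and inquiries are not in the hypothesis sentence.
- *The log is faulty because most contacts are ineligible.* That is also true at baseline: 26% of OTNY referrals are eligible, against 20% expected from the campaign.

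One further objection stands in part. Campaign contacts are screened by research staff before they reach OTNY, so some who drop out early will never appear in OTNY central. Counting from OTNY alone leaves them out. That is a real cost, but it suits a hypothesis about referrals and admissions to OTNY.

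**Conclusion.** The concern holds for inquiries and FEP referrals. As written, the plan compares counts ascertained in different ways in control and active cluster-periods, and the difference coincides exactly with treatment. This is a defect in a stated comparison, not just a missing detail.

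For inquiries, the comparison cannot be interpreted as a test, because the whole expected rise comes through the new source and its true part cannot be isolated. For FEP referrals, the possible distortion runs from none to an apparent ratio of 2.36 in place of 1.68, or to 1.68 in place of 1.00 if the campaign only re-routes patients. These sizes rest on two assumptions: that baseline FEP referrals are the 26% found eligible, and a duplicated share that the documents do not give.

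The change should be made, but the trial's main result does not depend on it. Hypothesis B is one of Aim 1's two hypotheses, and the power calculation covers Hypothesis A only.

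**What to change.** Rewrite the Hypothesis B comparison in Section 12 as follows.

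- Count FEP referrals and admissions from OTNY central only, in every cluster-period, with one written definition of an FEP referral and each person counted once.
- Use the campaign log to identify the source of a referral and to report campaign contacts descriptively, in persons as well as interactions.
- Do not test total inquiries against baseline.

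The main comparison needs only the OTNY data already promised and a change of wording. There are two costs. Campaign contacts who never reach OTNY will be described but not tested. Splitting active-period referrals by source may need a campaign tag or a matching field in the OTNY extract; the fields listed in Section 12 include neither, so this could mean an added intake item across the 21 sites. The main comparison does not depend on that tag.

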Searching online has become the primary resource for youth seeking out mental health information ¹⁴. This is especially true for stigmatized illnesses such as schizophrenia as the Internet provides a comfortable and anonymous setting to gather information about symptoms and treatment options ¹⁵. We demonstrated that participants with FEP reported utilizing the Internet first, and most frequently, to gather information prior to receiving psychiatric care while psychotic symptoms were emerging ^{16,17}. Youth with FEP were more likely to search online for information as opposed to, or prior to, discussing with peers, family, physicians, and mental health clinicians. Moreover, the Internet has increasingly become an important source of referrals to FEP programs ¹⁸. The Internet may represent one of the first proactive steps towards treatment initiation ¹⁶ and information gathered online appears capable of impacting mental health related help-seeking behavior ¹⁹.

There is an unexplored opportunity to harness the Internet's far reaching platform to improve early detection and intervention for psychosis. Given that adolescents and young adults in the early stages of psychotic illness, as well as their caregivers, are known to be online, searching for information, prior to receiving formal diagnoses and treatment, and throughout the DUP, we propose to capitalize on the immense power of existing and accessible online engagement tools in order to identify and meaningfully interact with patients with FEP and their caregivers, providing them with instant information and resources, designed to move them along their trajectory to care, and facilitate earlier linkage to specialty services.

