12. STATISTICAL ANALYSIS

- Describe how your data will be used to test the hypotheses.
- State clearly what variables will be tested and what statistical tests will be used.
- *Include sample size calculations.*
- If this is a pilot study, state which variables will be examined for hypothesis generation in later studies.

A stepped-wedge cluster randomization (CR) design will be implemented. After a baseline period of six months, two clusters (grouped clinics) will be randomly assigned in month 7 and by month 18, all of NYS will be running the campaign. This strategy allows each region to serve as its own control³⁷. The treatment effect can be modeled as a random effect at the cluster level which will accommodate treatment heterogeneity across the clinics. We grouped the 21 OTNY sites into 6 clusters based on geolocation as well as the total number of FEP referrals at each clinic between 10/01/2017 to 09/30/2018. We combined some regions to ensure that each cluster will be able to successfully meet recruitment criteria. The six clusters are; 1) Bronx, 2) Manhattan, 3) Queens, 4) Brooklyn, 5) Hudson River/Central NY, 6) Staten

Version Date: 6.9.22 Page 12 of 31

Island/Long-Island/Western NY. There will be a total of four 6-month time periods, including the baseline period where all 6 clusters receive the control treatment. All analyses for Aim 1 (hypotheses A and B) will be conducted within the Generalized Linear Mixed Models (GLMM) framework with an identity link for continuous outcomes and logit link for binary outcomes. Analyses for Aim 2 will be done using asymptotic z-tests for proportions after accounting for the variance inflation factors (VIF). Aim 3 is exploratory, and hence only 95% confidence intervals, accounting for VIFs, will be calculated for the rates.

Aim 1: Evaluate the effectiveness of a search engine ad campaign on reducing DUP and raising rates of FEP referrals by directly comparing DUP and FEP referrals pre and post campaign activation. Hypothesis A: Patients admitted to OTNY via campaign channels will demonstrate a significantly shorter DUP than those admitted to OTNY through traditional outreach prior to campaign activation.

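### Hypothesis B is worded as a before-versus-during comparison of statewide counts, and the Aim 1 model names neither a calendar-period effect nor a link for counts, so the concurrent randomised contrast is left unspecified

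*Combined protocol and SAP*

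**What the plan says.** The opening of section 12 sets the design: "A stepped-wedge cluster randomization (CR) design will be implemented". It continues: "There will be a total of four 6-month time periods", the first with all six clusters in control, and "two clusters (grouped clinics) will be randomly assigned in month 7". The benefit claimed is this: "This strategy allows each region to serve as its own control".

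The same paragraph puts all Aim 1 analyses, Hypotheses A and B alike, in a generalized linear mixed model framework, with an identity link for continuous outcomes and a logit link for binary ones. The only model feature described is permissive: "The treatment effect can be modeled as a random effect at the cluster level". No fixed effects are listed, and no link is given for counts or rates.

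Under Aim 1, Hypothesis B, the plan says "We will extract OTNY referral data from each site prior to activing the campaign to serve as baseline". The contrast follows: "We will compare baseline rates of inquiries, number of FEP referrals, and number of patients admitted to OTNY in NYS prior to campaign activation". The comparator is the same quantities statewide while the campaign is active, arriving through campaign and traditional channels. No calendar-time or secular-trend term appears anywhere in section 12. The section states that power was calculated for Hypothesis A only.

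**The concern.** In a stepped wedge, exposure and calendar time are tied together by design, because clusters only move from control to active. A comparison of before with during, whether statewide or within each region, therefore mixes the campaign effect with whatever else changed over those two years. Letting each region serve as its own control removes stable differences between regions. It does not remove a trend that all regions share.

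Staggered random start dates exist to separate the two, because in the second and third periods some clusters are active while others are not. That separation is obtained only if the model contains period effects. The Hypothesis B text describes a contrast without them, and the model paragraph does not supply them. If the analysis followed the wording, a campaign with no effect could be reported as having significantly increased referrals and admissions.

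**Working it through.** **1. The plan's own Aim 1 figure.** Section 12 gives mean DUP 179 weeks, SD 249, ICC 0.1, a 50% reduction (difference 89.5), 80% power, α 0.05, 6 clusters and 3 steps, with 32 per cluster per period as the result. Sidedness is not stated; two-sided is taken here, since one-sided gives 25.

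- Individually randomised: 2 × (1.960 + 0.842)² × (249/89.5)² = 121.5, so 122 per arm and 244 in total.
- Stepped-wedge design effect with k = 3 steps, one baseline period and one measurement per step, at n = 32: [1 + 0.1(96 + 32 − 1)] / [1 + 0.1(48 + 32 − 1)] × 3(0.9) / [2(3 − 1/3)] = (13.7/8.9) × (2.7/5.333) = 0.779.
- 244 × 0.779 / 6 = 31.7, so 32. The stated figure is reproduced.

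This formula presumes period effects. As a check, take the Hussey-Hughes variance with fixed periods, with I = 6, T = 4, U = 12, W = 0 + 4 + 16 + 36 = 56, V = 2(9 + 4 + 1) = 28, σ² = 0.9 × 249²/32 = 1,744 and τ² = 0.1 × 249² = 6,200:

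Iσ²(σ² + Tτ²) / [(IU − W)σ² + (U² + ITU − TW − IV)τ²] = 6 × 1,744 × 26,544 / (16 × 1,744 + 40 × 6,200) ≈ 1,007

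The SE is 31.7 weeks, and power at 32 is 80.5% (79.3% at 31). Without period effects, power at 32 would be 99.8%, and about 11 per cluster-period would be enough.

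**2. How far apart in time the compared cells are.** Two clusters start at each of three steps, so 0, 2, 4 and 6 of 6 clusters are active in periods 1 to 4. That is 12 active cells of 24, as section 12 states under Aim 2.

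| Clusters starting in | Mean control period | Mean active period | Gap |
|---|---|---|---|
| period 2 | 1 | 3 | 2 |
| period 3 | 1.5 | 3.5 | 2 |
| period 4 | 2 | 4 | 2 |

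The gap is two periods, or 12 months, in every cluster. With shared growth g per period and no campaign effect, a model with cluster effects but no period effects estimates exp[2 × log(1+g)] = (1+g)². This is 1.10 at 5% and 1.21 at 10%. Taking the statewide wording literally, baseline against the following 18 months gives nearly the same ratios (1.10 and 1.21).

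**3. False-positive rates.** Sections 5 and 8 give 34 referrals and 8 enrolments a week, so 34 × 26/6 = 147.3 and 8 × 26/6 = 34.7 per cluster-period. The assumptions are the growth g, an extra cluster-period CV, and a between-cluster log SD of 0.2. The simulation used 20,000 replicates per scenario, cluster effects plus a campaign indicator, and a two-sided t test at 0.05 on residual degrees of freedom. There was no true campaign effect. Rates without period terms:

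| Outcome | g | Poisson | CV 0.1 | CV 0.2 |
|---|---|---|---|---|
| Referrals | 2.5% | 24% | 12% | 7% |
| Referrals | 5% | 66% | 33% | 15% |
| Referrals | 10% | 99% | 81% | 42% |
| Admissions | 5% | 23% | 18% | 12% |
| Admissions | 10% | 65% | 51% | 32% |

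Admissions at 2.5% give 7% to 9%. With period terms the rate is about 5% in every row. Without growth, both models hold 5%.

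**The case against.** A reader might infer that the plan discards its randomised contrast. The documents do not support that. Section 12 places Hypothesis B in a mixed model under a stepped-wedge design, data are extracted by site, and a framework sentence that lists no fixed effects leaves period terms open without excluding them. With staggered starts there is no single statewide activation date, so the before/during wording may be meant cluster by cluster. The Hypothesis A sample size needs period effects, which suggests that a period-adjusted model was intended. All of this stands, and it limits the point to what is not specified. It does not rescue the stated contrast: read within clusters or statewide, that contrast is confounded with time. The sizing covers Hypothesis A alone and was not carried into the analysis text.

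A reader might also infer from section 3 that the plan documents rising referral volume: "the Internet has increasingly become an important source of referrals to FEP programs". That sentence concerns the channel and is compatible with substitution between channels. The documents give no OTNY growth rate. At 2.5% growth the effect on admissions is small, and imitating the forecast enrolment ratio of 12/8 = 1.5 would take about 22% per period (1.22² ≈ 1.49).

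Campaign-channel referrals are recorded separately, so a campaign that drew nobody would be visible. This is a useful diagnostic, but it is not a trend adjustment of the total counts being tested.

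Finally, the simulation leaves out a cluster-specific campaign effect, which the plan allows. A cluster-level before/after t test on 5 degrees of freedom, which accommodates one, gives 35% in place of 42% for referrals at g = 10% and CV 0.2. The rates fall slightly and the conclusion is unchanged.

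**Conclusion.** The point holds as a gap in specification together with a biased stated contrast. The Aim 1 model text gives no period effect and no count link, and the Hypothesis B sentence describes a comparison that credits shared growth to the campaign by about (1+g)². The factor follows from the roll-out alone, taking two clusters at each of three steps. The false-positive rates rest on assumed growth and overdispersion, and should be read as a range. The missing period term sits in model text shared with Hypothesis A, where it also leaves the analysis out of step with the plan's own sizing. This should be corrected before analysis: Hypothesis B makes a claim of significance, although it is not the powered primary outcome.

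**What to change.** In the opening of section 12, state that the Aim 1 mixed model includes categorical effects for the four six-month periods, a cluster random effect, and a campaign indicator defined by cluster and period. For Hypothesis B, add a count model (Poisson or negative binomial, log link) on cluster-by-period counts, with a small-sample correction for six clusters. In the Hypothesis B paragraph, name the campaign coefficient from this model as the estimate, and keep the statewide before/during totals as description.

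This is a few sentences of text and three more parameters per model, with the same data and no extra recruitment. The cost is precision. At the plan's forecasts, power for referrals (34 to 64 a week) stays at 94% or more on the log scale. For admissions (8 to 12 a week) it falls from about 100% to 87% under Poisson variation, from over 99% to 74% at CV 0.1, and from 92% to 48% at CV 0.2. The higher figures apply only if there is no trend. The plan states no power for Hypothesis B, so no stated figure is breached, but the likely precision for admissions should be acknowledged.

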the course of illness development, as well as individuals who might not otherwise come into contact with traditional referral sources. In response to this challenge, Northwell Health's early psychosis research team is collaborating with Strong365, a nonprofit initiative dedicated to raising early psychosis intervention awareness, to develop and test a proactive and targeted comprehensive digital media marketing campaign designed to facilitate help-seeking and encourage treatment initiation in prospective patients with FEP and their caregivers. Our team will take advantage of search engine advertising, which allows advertisers (researchers) to select keywords/phrases and create linked advertisements appearing as a strategically placed search result. Our dedicated ads will appear in response to online search queries conducted by prospective patients and their caregivers throughout New York State (NYS) that align with the campaign's pre-selected keywords/phrases. Individuals who click on the ads will be immediately directed to our campaign landing page/website, and offered a variety of established, innovative, and interactive online engagement tools intended to instantly connect users with coordinated specialty care (CSC) staff and to facilitate earlier treatment initiation.

Campaign referrals will be centralized and individuals with FEP will be enrolled into OnTrackNY (OTNY), a network of 21 dedicated early psychosis intervention programs throughout NYS. The campaign will target individuals as well as their friends, family, and caregivers, searching for information online. We will measure the DUP of individuals enrolled into OTNY before and after campaign activation and track the impact of the campaign on the number of FEP referrals and number of patients admitted to OTNY in NYS. Furthermore, we aim to identify the campaign target audience most effective at promoting treatment initiation as well as the online tools and resources most effective at encouraging treatment initiation of identified individuals with FEP. We will additionally explore the online trajectories to care of individuals with FEP engaging with the campaign.

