8. NUMBER OF SUBJECTS

- Indicate the total number of subjects to be accrued locally. If applicable, distinguish between the number of subjects who are expected to be pre-screened, enrolled (consent obtained), randomized and complete the research procedures.
- If your study includes different cohorts, include the total number of subjects in each cohort.
- If this is multisite study, include total number of subjects across all sites.

OTNY receives on average 34 referrals weekly, of which, on average 26% are found eligible, and 8 new FEP patients are enrolled in NYS each week. Based on existing OTNY inquiry data as well as the results of our prior pilot initiatives, we anticipate approximately doubling weekly inquiries as a result of the campaign, arriving through campaign related channels over the course of the trial (30 additional referrals). Of those, we anticipate that 20% will be appropriate for OTNY (6 participants weekly) and that 4 of those individuals will be successfully enrolled each week as a result of the campaign.

Version Date: 6.9.22 Page 9 of 31

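### Hypothesis B appears to place admissions by admission date with no transition window, which pulls the admissions effect towards zero by an amount that depends on an intake delay the plan does not give

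*Combined protocol and SAP*

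**What the plan says.** Section 12, Aim 1, Hypothesis B, sets counts before activation against counts during the campaign. On the control side the admissions count is the "number of patients admitted to OTNY in NYS prior to campaign activation, to rate of inquiries" part of the sentence. On the campaign side it is the "number of patients admitted to OTNY in NYS while the campaign is active both arriving through the campaign, and traditional referral channels". All channels are pooled on the campaign side.

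The same section puts steps between referral and admission: "All FEP referrals will be provided an appointment for an evaluation at the nearest OTNY program and admission to the program will be recorded". No section gives the usual time between the two, and none mentions a lag, a washout or a transition window.

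The layout is a stepped wedge: "There will be a total of four 6-month time periods, including the baseline period where all 6 clusters receive the control treatment". The roll-out is described as "two clusters (grouped clinics) will be randomly assigned in month 7 and by month 18, all of NYS will be running the campaign". Aim 1 is to be analysed with generalized linear mixed models, and the treatment effect may be random by cluster. Period effects are not mentioned, and only identity and logit links are named. Section 12 limits the power analysis to Hypothesis A.

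**The concern.** In both count phrases the time qualifier is attached to being admitted. Read that way, a patient who was referred through a traditional channel shortly before activation, and admitted shortly after it, is a campaign-period admission although the campaign played no part. In the same weeks the campaign's own referrals are still waiting for evaluation. The first weeks of each active phase therefore look like control weeks.

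This happens once in every cluster, in its first active period. A stepped-wedge analysis with period effects leans heavily on that period, so the loss can exceed the plain share of misplaced patients. The bias is towards no effect. At stake is an understated gain in admissions, in a hypothesis for which the plan shows no power margin.

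**Working it through.** **Inputs from the documents**
- Layout (section 12): 6 clusters, 4 periods of 6 months (26 weeks), 2 clusters switching at each of 3 steps. Active cells: 2×3 + 2×2 + 2×1 = 12 of 24. First active cells: one per cluster, so 6 of the 12.
- Baseline admissions (section 8): "8 new FEP patients are enrolled in NYS each week".
- Expected gain (section 12): "4 of those individuals will be successfully enrolled each week as a result of the campaign". So 8 becomes 12 per week, a rate ratio of 1.50.

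**Assumptions, not in the documents**
- Referral-to-admission delay L of 2, 4, 6 or 8 weeks.
- Period effects in the model: shown both with and without.
- Correlation between period means of one cluster: varied from 0 to 0.99, because no intracluster correlation is given for admission counts.

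**Step 1. The plan's own Aim 1 figure.** Hypothesis B has no stated sample size, so the only figure to reproduce is the one for Hypothesis A. With a 50% reduction of 179 weeks (89.5), SD 249, two-sided 0.05 and 80% power:
- individually randomised n per arm = 2 × (1.960 + 0.842)² × 249² / 89.5² = 121.5, so 243.0 in total;
- stepped-wedge design effect with ICC 0.1 and m per cell = [1 + 0.1(4m − 1)] / [1 + 0.1(2.5m − 1)] × 3(0.9) / [2(3 − 1/3)];
- at m = 32: (13.7 / 8.9) × 0.50625 = 0.779. Required: 243.0 × 0.779 × 4 = 757, and 24 × 32 = 768 suffices. At m = 31 the requirement is also about 757, but 24 × 31 = 744 falls short.

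So 32 per cell and 768 in total are reproduced. This confirms the layout. The design effect used here assumes period effects.

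**Step 2. What a delay does.** If campaign-generated admissions start L weeks after activation, the first active cell of each cluster shows 1 − L/26 of the effect and later active cells show all of it. If w is the total weight that the estimator puts on first active cells, the share of the effect lost is

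loss = w × L/26.

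**Step 3. The weight w.**
- Without period effects: w = 0.50 for the plain mean of active cells minus control cells (6 of 12), rising to 0.60 with a cluster random intercept.
- With period effects and a cluster random effect, with or without a random treatment effect: w = 0.75 (correlation 0) to 1.21 (correlation 0.99). It can exceed 1 because the third period of exposure then gets a negative weight. At correlation 0.99 without a random treatment effect, the weights on the first, second and third exposure periods are 1.198, 0.101 and −0.299.

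**Step 4. Results**

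| Assumed delay L (weeks) | L/26 | Loss without period effects (w 0.50-0.60) | Loss with period effects (w 0.75-1.21) |
|---|---|---|---|
| 2 | 0.077 | 4-5% | 6-9% |
| 4 | 0.154 | 8-9% | 12-19% |
| 6 | 0.231 | 12-14% | 17-28% |
| 8 | 0.308 | 15-18% | 23-37% |

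Example, L = 4: 0.50 × 0.154 = 7.7%, 0.75 × 0.154 = 11.5% and 1.21 × 0.154 = 18.6%. An exponentially distributed delay with the same mean gives nearly the same losses.

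**Step 5. On the plan's expected numbers.** The plain before/after mean estimates 4 × (1 − 0.5 × L/26) added admissions per week: 3.85, 3.69, 3.54 and 3.38 for the four delays, instead of 4. A Poisson model with fixed cluster and period effects (a log link, which the plan does not name) estimates rate ratios of 1.45, 1.40, 1.35 and 1.31 instead of 1.50.

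**The case against.** The strongest reply is that the plan never states a counting date. The OTNY data to be extracted are referral records, and the outcome of the referral, including intake, is a field on them. One could count admissions as outcomes of the referrals received in each period, and then there is no bias. This stands in part: admission-date counting is the plain reading of the comparison sentence, not an explicit rule. It does not remove the point, because nothing in the plan directs the analyst to the referral-based count.

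A reader might infer that a few weeks of intake delay is known to remove a tenth to a third of the effect. The documents do not support that. They give no delay, and they do not state period effects. A loss of that order needs roughly 3 to 8 weeks together with period effects. For the direct before/after comparison that the text describes, the loss is 4-18% over 2 to 8 weeks.

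It is also fair to say that the consequence is limited. Inquiries and FEP referrals, compared in the same sentence, are dated at contact and are unaffected. Hypothesis A is the powered outcome, and its sample size does not depend on this. A bias towards no effect does not produce a false positive.

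A reader might also see a conflict between activation by month 18 and four 6-month periods. The end of month 18 is the start of month 19, so the two can describe one boundary, and nothing here rests on it.

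Finally, the obvious remedy has its own risk. Visitors may return to the site repeatedly and may stay anonymous. A clock started at first online contact would not match one started at a clinic referral. That objection stands and shapes the fix.

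**Conclusion.** The point holds in a limited form. On its plain reading, the plan places admissions by admission date with no transition window, and this biases the admissions part of Hypothesis B towards no effect. The direction follows from the order of events that the plan itself describes and does not depend on the model.

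The size is conditional. It runs from about 4% (2 weeks, no period effects) to about 37% (8 weeks, period effects and high within-cluster correlation). Both the delay and the period effects are assumptions. The stepped-wedge design makes period effects the natural choice, but section 12 should say so. This should be corrected before analysis; it does not invalidate the trial or its primary comparison.

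**What to change.** For Hypothesis B, place each admission in the cluster-period of its OTNY referral date, defined the same way for campaign and traditional channels, and not by first online contact. Count admissions that occur within one fixed window of that date, with the same window in every period, and follow referrals from the fourth period into Phase 3, which lasts 6 months. Report the observed referral-to-admission delay. State whether the model includes period effects.

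First confirm that the OTNY extract holds a referral date. Section 12 does not name one among the extracted items, although the weekly referral counts in section 8 suggest that one exists. If it cannot be obtained, exclude a fixed transition window after each activation, at least as long as the usual delay, and analyse admissions per week observed because the first active cells become shorter.

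The cost is a change of analysis wording and a short additional extract. Final admission counts arrive about one window later, and admissions after the window (or in the excluded transition weeks) are not counted.
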